#### Other prohibited concomitant medications:

Patients should not receive any chemotherapy, anticancer immunotherapy, other investigational therapy or other JAK2 inhibitors whilst on trial treatment. Cytoreductive treatment is also prohibited throughout the trial with the exception of hydroxycarbamide and anagrelide, which can be used to control blood cell counts or manage aggressive disease following consultation with the Chief Investigator for a period not exceeding 28 days. Hydroxycarbamide or anagrelide prescribed prior to study entry must be stopped before the first scheduled day of trial treatment.

Splenic irradiation is prohibited throughout the trial. Sites are requested to obtain prior CI approval via the trials office before administering any other radiotherapy treatment.

#### Prohibited foods:

Grapefruit products (including juice) and Seville oranges (including marmalade) should be avoided for the duration of the trial.

Please refer to the prohibited concomitant medication list as detailed in Appendix 5.

The Sponsor must be notified in advance (or as soon as possible thereafter) of any instances for which prohibited therapies are administered.

#### **Observational Component**

All concomitant medication is permitted.

# 7.12 Patient Follow Up

#### Interventional Component

Patients who are gaining clinical benefit at the end of 6 cycles may continue to receive therapy with 5azacitidine and/or ruxolitinib at the discretion of the CI until loss of response or unacceptable toxicity. Patients that have to discontinue the combination therapy due to a toxicity that is clearly related to just one of the trial treatments may continue to take the alternative medication as long as they continue to obtain a clinical benefit in the view of the local investigator and the Chief Investigator (section 7.8.1). Patients will be followed-up for survival data for a minimum of 1 year from the date of start of treatment.

All patients must have a final assessment 28 days after the last dose of trial medication.

### **Observational Component**

After the 6 month study period patients will be followed up for data on further treatments and response and survival data for a minimum of 1 year from the date of registration.

# 7.13 Treatment Discontinuation and Patient Withdrawal

In the event of discontinuation of study treatment, e.g. unacceptable toxicity or patient choice, full details of the reason/s for discontinuation should be recorded on the CRF.

All patients, including non-compliant subjects, should be followed up according to the protocol unless they withdraw specific consent.

In the event of a patient's decision to withdraw from the trial, the Investigator should ascertain from which aspects of the trial the patient wishes to withdraw and record the details on the appropriate CRF. All information and blood/tissue samples collected up until the point of retraction will be retained and analysed. If a patient chooses to withdraw from treatment only (interventional arm only), the patient should discontinue treatment and continue to be assessed in accordance with the protocol. If a patient wishes to withdraw from the trial (i.e. including trial specific assessments), but is willing for further data to be supplied to the Trials Office, then further routine 'follow-up' data (e.g. toxicity data) will continue to be supplied by the Investigator to the Trials Office.

#### Interventional Component

Patients who stop treatment due to adverse experiences (clinical or laboratory) will be treated and followed according to accepted medical practice. All pertinent information concerning the outcome of such treatment must be recorded in the CRF.

The following are justifiable reasons for the Investigator to stop study treatment:

- Unforeseen events: any event which in the judgement of the Investigator makes further treatment inadvisable
- Serious violation of the trial protocol (including persistent patient non-attendance and persistent non-compliance)
- Stopping by the Investigator for clinical reasons not related to the study drug treatment

Patients must stop study treatment in the event of:

- Occurrence of a DLT
- Unacceptable toxicity
- SAE requiring permanent discontinuation of treatment
- Occurrence of pregnancy in female participant

# 8. ADVERSE EVENT REPORTING

The collection and reporting of AEs will be in accordance with the Medicines for Human Use Clinical Trials Regulations 2004 and its subsequent amendments. Definitions of different types of AE are listed in Appendix 3. The Investigator should assess the seriousness and causality (relatedness) of all AEs experienced by the patient (this should be documented in the source data) with reference to the SPC.

# 8.1 Reporting Requirements – Interventional Component

# 8.1.1 Adverse Events

All medical occurrences which meet the definition of an AE (see Appendix 3 for definition) should be reported. Please note this does not include abnormal laboratory findings. An abnormal laboratory value is only considered to be an AE if the abnormality:

- Results in early discontinuation from the study treatment and/or
- Requires study drug dose modification or interruption, any other therapeutic intervention or is judged to be of significant clinical importance

If a laboratory abnormality is one component of a diagnosis or syndrome, then only the diagnosis or syndrome should be recorded.

Pre-existing conditions should only be reported if the condition worsens by at least 1 CTCAE grade. Details of all AEs experienced by the patient should be recorded in the hospital notes.

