5-azacitidine is licensed and approved for treatment of adult patients who are not eligible for HSCT with high risk myelodyplastic syndromes (MDS), where it has been documented to improve survival [7]; low-blast count (20-30%) AML; and AML with >30% marrow blasts. There are few reports of its use in MPNs however (either chronic phase or advanced phase). Considerable haematological toxicity was noted in a Phase 2 study of 5-azacitidine in MF at the standard licensed dose (75 mg/m2 for 7 days every 4 weeks, with 29% grade 3/4 neutropenia). Responses were seen in 24% of patients, however no CRs were reported, and no impact on marrow fibrosis was observed [8]. Median time to response was 5 months, in keeping with treatment results in MDS where prolonged therapy is necessary. Interestingly global DNA-hypomethylation was documented in sequential patient samples. Hypermethylation of promoter regions of tumour-related genes is however rare in early-phase MF suggesting that methylation of cell-cycle control genes is unlikely to drive the pathogenesis of the disease at diagnosis. However, hypermethylation of the P15INK4b and P16INK4a genes in MF in transformation to AML has been frequently observed, and might be a legitimate therapeutic target [9]. Furthermore, sequential treatment with demethylating agents (decitabine) followed by HDAC inhibitors has been shown to eliminate JAK2+ marrow repopulating cells in NOD/SCID mice[10]. A recent historical treatment cohort from the Groupe Francophone des Myelodysplasies (GFM) (54 patients) describes the efficacy of 5-azacitidine in advanced phase MPN or AML secondary to MPN [4]. An overall response rate of 54% was observed, with 24% CR rate. Higher responses were seen in advanced phase than established AML (36% CR vs. 14% CR respectively). Small series of patients treated with decitabine have also been described (in both chronic phase IMF and advanced phase), including 2 of 4 patients with blast crisis MPN who achieved CR [11, 12]. These data are certainly encouraging for further studies.

It is clear from the limited clinical data available thus far that monotherapy of advanced phase MPNs / secondary AML with either of these agents is unlikely to produce significant and durable responses for a majority of patients. Combination therapy is attractive to fully exploit their differing mechanisms of action. There are currently very few therapeutic options available for this patient group.

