#### Cytopenias

Cytopenias will not be an indication for dose delay. MPN-BP is often associated with profound peripheral cytopenia (neutropenia, thrombocytopenia or anaemia). Patients who have these features at baseline or who develop these whilst on treatment may receive supportive care in the form of red cell or platelet transfusion or growth factor support at the local Investigator's discretion.

5-azacitidine and ruxolitinib are associated with cytopenias and bone marrow suppression and dose modifications are not scheduled for these events. In the event of severe bone marrow suppression or cytopenias following acquisition of a clinical response and not considered disease related, the CI must be informed to decide an appropriate course of action. Complete blood counts will be performed as per the above schedule, and at other time-points according to investigator discretion.

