# **12.2 Definition of Outcome Measures**

#### 12.2.1 Interventional Component

#### **12.2.1.1 Primary outcome measures**

MTD of ruxolitinib in combination with 5-azacitidine in patients with advanced phase MPNs as defined by the number of reported DLTs (as defined in section 2.2) occurring within the first cycle of treatment (first 28 days).

Safety of ruxolitinib in combination with 5-azacitidine will be assessed using the CTCAE v4.0 criteria.

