#### Interventional component

Primary outcome measure

• The MTD, defined as the dose level with an associated DLT probability over the first cycle of treatment (28 days) closest to the target DLT rate of 25%, will be reported with its associated probability of DLT and 90% probability interval.

Secondary outcome measures

- Best response following 3 and 6 cycles of treatment will be reported as the number and proportion of patients in each response category and overall.
- DLTs and AEs (according to the CTCAE criteria version 4.0), records of blood and platelet transfusions, physical examinations to assess spleen and liver size, blood counts (including haemoglobin and platelet count, quality of life questionnaires and survival data) will be collected and reported in a descriptive manner.

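### The AE rule lets grade 3/4 cytopenias into the CTCAE safety data mainly through local treatment or judgement, and the protocol specifies no grading of the scheduled blood counts

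*Protocol*

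**What the plan says.** Section 2.1 puts safety beside the MTD in the primary objective, and section 12.2.1.1 lists it under the primary outcome measures: "Safety of ruxolitinib in combination with 5-azacitidine will be assessed using the CTCAE v4.0 criteria".

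Section 8.1.1 defines what sites report. Of the AE definition it says "Please note this does not include abnormal laboratory findings", and then gives the exceptions. The first is "Results in early discontinuation from the study treatment and/or"; the second is "Requires study drug dose modification or interruption, any other therapeutic intervention or is judged to be of significant clinical importance". If the value is part of a diagnosis or syndrome, only that diagnosis is recorded. On conditions already present, "Pre-existing conditions should only be reported if the condition worsens by at least 1 CTCAE grade". Appendix 3 repeats the laboratory exclusion without the exceptions.

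On cytopenias, section 7.8.2 rules out dose delay and states that "5-azacitidine and ruxolitinib are associated with cytopenias and bone marrow suppression and dose modifications are not scheduled for these events". Transfusion and growth factors are left to the local investigator. The DLT definition in section 2.2 covers non-haematological toxicity only, and also exempts febrile neutropenia.

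For analysis, section 12.3 lists "DLTs and AEs (according to the CTCAE criteria version 4.0), records of blood and platelet transfusions", organ size, blood counts, quality of life and survival, all to be reported descriptively. Section 12.2.1.2 fixes the count outcomes as mean change in haemoglobin and in platelets from baseline to days 22-25 of cycles 3 and 6.

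**The concern.** The protocol treats marrow suppression as an expected effect of both drugs. Its Background adds that "Considerable haematological toxicity was noted in a Phase 2 study of 5-azacitidine in MF", with 29% grade 3/4 neutropenia. Haematological toxicity is therefore something a reader of the safety result will look for.

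Since it cannot be a DLT, the MTD carries no information about it, and the graded safety data are where it would have to appear. If entry to those data depends on whether a site transfused, gave growth factor or thought the value important, two sites with the same counts can report different AE rates. The same uncertainty would reach the safety data that the Trial Steering Committee reviews after each cohort (section 13.4), and the judgement of tolerability that section 1.1 says could lead to a phase II trial.

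**Working it through.** The protocol states no figure on this point, so there is none to reproduce. The check takes each route by which a grade 3/4 cytopenia could reach the AE data and asks whether it applies.

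1. **Early discontinuation (8.1.1).** Open, but no cytopenia threshold triggers it.
2. **Dose modification or interruption (8.1.1).** In cycle 1 no dose modification is permitted (7.8.1). Later, cytopenias are no reason for delay and have no scheduled modification. Two discretionary routes remain in 7.8.2: dose reduction for unacceptable toxicity, and referral to the Chief Investigator for severe suppression that follows a response and is not thought disease-related.
3. **Other therapeutic intervention (8.1.1).** Open. Transfusion or growth factor (7.8.2, 7.10) would qualify, and both follow local discretion.
4. **Judged clinically important (8.1.1).** Open and needs no action, but depends on the investigator.
5. **Worsening of a pre-existing condition (8.1.1).** At least one CTCAE grade is needed. This matters because 7.8.2 notes that blast-phase disease often brings profound cytopenia.
6. **DLT (2.2).** Closed.

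The routes that usually work without opinion (a DLT, or a protocol-triggered dose change) are closed or discretionary. An untreated, asymptomatic grade 3/4 count that the investigator does not think important reaches no AE form.

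Next, what is collected compared with what the analysis text fixes:

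- Section 7.5.5 requires full blood counts, including absolute neutrophils, weekly in cycle 1 (days 1, 8, 15 and 22) and on days 1, 8 and 22 of cycles 2-6. That is 4 + (5 × 3) = 19 scheduled on-treatment counts over six cycles, plus baseline and end of study.
- The mean-change outcomes use baseline and 2 of those 19 counts. None of the 2 is in cycle 1.
- They cover haemoglobin and platelets, not neutrophils.
- A mean does not give the number of patients who reached grade 3 or 4, and a late value is not a worst value.
- In 12.3 CTCAE is attached to DLTs and AEs. Blood counts come later in the same list, with no grading mentioned.

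The data needed for an unselected graded summary are therefore already collected, but the analysis text does not commit to one.

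On size, the number shown in an AE table would be (patients with grade 3/4 cytopenia) × (share meeting an 8.1.1 criterion). The protocol gives neither factor for this combination in this population, so the shortfall cannot be calculated.

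**The case against.** The best case against is that this belongs in the SAP, which is not shown. Section 12.2.1.1 does not confine CTCAE assessment to AE forms, counts are reported descriptively, and the wording in 12.3 on counts is not exhaustive. The protocol does not rule out a graded table. That much stands. It does not fully answer the point, because the protocol itself sets the AE rule, ties CTCAE to DLTs and AEs, and fixes the count outcomes. A SAP that kept strictly to that text could omit a graded haematological table from a primary safety outcome.

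It is also fair to say that transfusions are recorded throughout (7.5.9), that transfusion dependence has fixed thresholds compared with baseline (12.2.1.2), and that febrile neutropenia and infections are clinical diagnoses reportable in their own right. These give partial information, but not neutrophil grades.

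Four stronger readings might be inferred and are not supported:

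- *Cytopenias are reported only if someone acts on them.* The clinical-importance criterion needs no action.
- *Haematological toxicity will be under-reported, and no graded summary is planned.* The text shows that AE tables can understate it and that no graded summary is specified. It shows no more than that.
- *Cytopenia is the main known toxicity of the combination.* The protocol does not rank toxicities, and the three combination patients described in section 1.2.3 had minimal haematological toxicity.
- *The AE table would show 7-22% instead of 29%.* This takes 34 × 0.29 = 9.86 patients and assumes that 25% to 75% are captured: 9.86 × 0.25 = 2.5 (7% of 34) and 9.86 × 0.75 = 7.4 (22% of 34). The arithmetic is right, but the capture range is assumed and the 29% is for azacitidine alone in myelofibrosis. It illustrates the mechanism and is not an estimate.

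**Conclusion.** The point holds as a weakness in how a primary safety outcome is measured and summarised. Followed as written, the CTCAE-graded part of the safety result captures cytopenia chiefly through local treatment and judgement, so it can be incomplete and vary by site. The fixed count outcomes do not make up for this. Direction is clear for the AE table (it can miss events, and the rule does not add any); size is unknown.

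The conclusion rests on reading 8.1.1, 7.8.2, 2.2 and 12.3 together, and on the assumption that some grade 3/4 counts are neither treated nor judged important. If the SAP already grades the scheduled counts, what remains is to bring the protocol text into line. The separate handling of cytopenia for AE reporting, DLTs and dosing is a stated design choice and is not criticised here.

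**What to change.** In section 12.3, state that the worst CTCAE v4.0 grade for neutrophils, platelets and haemoglobin will be derived centrally from all scheduled blood counts. Report it for cycle 1 and overall, as a shift from baseline grade, and by ruxolitinib dose level. The shift from baseline is needed because many patients may enter with cytopenia. Show the table beside the AE table and in the reports to the Trial Steering Committee after each cohort.

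Leave the site AE-reporting rule, the DLT definition and all dosing rules unchanged.

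The cost is a little more analysis work on counts already collected, with no extra tests and no added site reporting. The drawback to accept is that reported grade 3/4 haematological rates may look less favourable than the AE table alone would.

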#### 8.1.2 Serious Adverse Advents

Investigators should report AEs that meet the definition of a Serious Adverse Event (SAE) (see Appendix 3 for definition) and are not excluded from the reporting process as described below.

#### 8.1.2.1 Events that do not require reporting on a Serious Adverse Event Form

The following events should not be reported on an SAE Form:

- Hospitalisations for:
  - o Pre-planned elective procedures unless the condition worsens

#### 8.1.2.2 Monitoring pregnancies for potential Serious Adverse Events

It is important to monitor the outcome of pregnancies of patients in order to provide SAE data in the case of congenital anomalies or birth defects.

In the event that a patient or their partner becomes pregnant during the SAE reporting period please complete a Pregnancy Notification Form (providing the patient's details) and return to the Trials Office as soon as possible. If it is the patient who is pregnant provide outcome data on a follow-up Pregnancy Notification Form. Where the patient's partner is pregnant consent must first be obtained and the patient should be given a pregnancy release of information form to give to their partner. If the partner is happy to provide information on the outcome of their pregnancy they should sign the pregnancy release of information form. Once consent has been obtained provide details of the outcome of the pregnancy on a follow-up Pregnancy Notification Form. If appropriate also complete an SAE Form as detailed below.

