# 4.2 Exclusion Criteria

#### Interventional Component:

- Any co-morbidity that could limit compliance with the trial or any other condition (including laboratory abnormalities) that in the Investigators opinion will affect the patient's participation in this trial
- New York Heart Association Class II, III, or IV congestive heart failure

- On-going cardiac dysrhythmias of grade 3, QTc prolongation >480 ms, or other factors that increase the risk of QT interval prolongation (e.g. heart failure, hypokalemia defined as serum potassium <3.0 mEq/L, family history of long QT interval syndrome)

- Erythropoietic agent within 28 days prior to registration
- Thrombopoietic agent within 14 days prior to registration
- Potent CYP3A4 inhibitor within 7 days prior to registration
- Experimental treatment within 14 days prior to registration
- Previous treatment for MPN-AP or MPN-BP, including stem cell transplant and low intensity AML chemotherapy
- Previously received 5-azacitidine. Ruxolitinib can be taken up until study entry at the pre-study dose. Hydroxycarbamide prescribed prior to study entry must be stopped before the first scheduled day of trial treatment
- Known contraindications to receiving 5-azacitidine or ruxolitinib
- Active infection ≥ grade 3 (CTCAE criteria) at trial entry
- Known HIV seropositivity
- Known to have active hepatitis A, B, or C
- Women who are pregnant or lactating. Patients of childbearing potential must have a negative pregnancy test prior to study entry
- Patients and partners of childbearing potential not willing to use effective contraception for the duration of the study treatment and for three months after the last dose

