#### 7.5.4 Pregnancy testing and contraception

A pregnancy test (serum/urine) for females of child bearing potential must be performed within 7 days prior to registration.

Females of childbearing potential: Must have a negative pregnancy test and should not be breastfeeding. Females must agree to use a reliable form of contraception during the trial and for at least three months after treatment has finished.

Males (whose partner may become pregnant): Must agree to use a reliable form of contraception or during the trial and for three months after treatment has finished.

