#### 8.1.3 Reporting period

Details of all AEs and SAEs (except those listed above) will be documented and reported from the date of commencement of protocol defined treatment until 28 days after the administration of the last treatment. SAEs that are judged to be at least possibly related to any of the trial IMPs must still be reported in an expedited manner irrespective of how long after IMP administration the reaction occurred.

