# 8.2.2 Reporting period

SAEs related to trial specific procedures will be documented and reported from the date of registration until 28 days after completion of the last protocol assessment.

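### Pregnancy notification ends 28 days after the last treatment, although the protocol requires contraception for three months after the last dose

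*Protocol*

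**What the plan says.** Four parts of the protocol bear on this point.

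- **Trigger for notification (Section 8.1.2.2).** "In the event that a patient or their partner becomes pregnant during the SAE reporting period please complete a Pregnancy Notification Form". Outcome data follow on a further form. For a male patient's partner, her consent and a signed release of information are needed first. The section gives its purpose as supplying serious-event data on birth defects.
- **Length of the window (Section 8.1.3).** Adverse events and serious adverse events are collected "from the date of commencement of protocol defined treatment until 28 days after the administration of the last treatment". There is one exception: serious events judged at least possibly related to a trial drug "must still be reported in an expedited manner irrespective of how long after IMP administration the reaction occurred".
- **Contraception period (Sections 4.2 and 7.5.4).** Section 4.2 excludes those who could conceive, or whose partner could, if they are "not willing to use effective contraception for the duration of the study treatment and for three months after the last dose". Section 7.5.4 adds, for women, "Females must agree to use a reliable form of contraception during the trial and for at least three months after treatment has finished", and for men with a partner who could conceive, "Must agree to use a reliable form of contraception or during the trial and for three months after treatment has finished".
- **Definition of a serious event (Appendix 3).** A congenital anomaly or birth defect is listed as a serious adverse event.

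No other section extends pregnancy notification beyond the 28 days.

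**The concern.** The protocol sets two periods after the last dose that concern pregnancy. During the longer one, patients and partners are asked to avoid conception. During the shorter one, the site must report a conception if it happens. Where the first continues after the second has ended, the protocol still asks for contraception but no longer asks what happened if it failed.

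What is at stake is the completeness of the pregnancy outcome data. Without a notification, no outcome form is due, and the consent and release step for a partner never starts. Normal outcomes are then not recorded. Losses that are not judged related, and anomalies the site never hears of, are also absent from the safety report. The report could not say how many pregnancies began in the rest of the three months or how they ended.

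**Working it through.** The protocol states no figure for this gap, so there is none to reproduce. The check is interval arithmetic on its own periods.

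**Inputs**
- End of pregnancy notification: 28 days after the last treatment (Sections 8.1.2.2 and 8.1.3 read together).
- End of contraception: three months after the last dose (Section 4.2), or after treatment has finished (Section 7.5.4, which says at least three months for women).
- Planned treatment: six cycles of 28 days (Section 3.1), so 6 × 28 = 168 days.
- Assumptions: three months is about 91 days, and both clocks start from the same last dose.

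**Uncovered share of the post-treatment contraception period**

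Uncovered days = contraception days − 28; share = uncovered days ÷ contraception days.

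| Three months taken as | Uncovered days | Share |
|---|---|---|
| 84 days (3 × 28) | 56 | 66.7% |
| 89 days | 61 | 68.5% |
| 91 days | 63 | 69.2% |
| 92 days | 64 | 69.6% |

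The choice of month length moves the result only between 67% and 70%.

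**Uncovered share of the whole period, on and after treatment**

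63 ÷ (168 + 91) = 63 ÷ 259 = 24%, if six cycles are given without delay.

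**What remains reportable on days 29 to 91**
1. A pregnancy begins after day 28. Section 8.1.2.2 requires no form, because the event is outside the period defined in Section 8.1.3.
2. If a congenital anomaly later becomes known to the site, it is a serious event under Appendix 3.
3. If it is also judged at least possibly related to a trial drug, the exception in Section 8.1.3 makes it reportable.
4. Steps 2 and 3 depend on the site learning of the outcome, and nothing in the protocol obliges it to ask.

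**Does existing follow-up reach far enough?** Section 7.12 follows patients for survival for at least one year from the start of treatment. Six cycles plus three months is 259 days, inside 365. The one-year minimum ends before the contraception period does once treatment lasts longer than 365 − 91 = 274 days, a little under ten 28-day cycles (274 ÷ 28 = 9.8). Section 7.12 permits treatment beyond six cycles, so this can occur.

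**The case against.** The strongest reply is that Section 8.1.2.2 exists to obtain data on birth defects, and that these stay reportable indefinitely under the exception in Section 8.1.3. This stands in part. A reader might infer that pregnancies beginning after day 28 are never followed; the documents do not support that, because a related serious event can still reach the safety database. The exception does not close the gap, however. It acts on an event already known and already judged related, whereas notification is the step by which the site comes to know.

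A second reply is that a contraception period and a reporting window serve different purposes, and no section says they must be equal. That is correct. This is a gap in what is collected and not a contradiction in the text. Nor do Sections 4.2 and 7.5.4 state how long drug exposure or reproductive risk lasts, so a reader should not infer that a conception on days 29 to 91 is shown to be drug-exposed.

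A third reply is that 69% is a share of days and not of expected events. This also stands. Section 1.1 cites median ages of 64 and 68.5 years in two large cohorts, so pregnancies will be few, although entry is open from age 16 and the contraception rule extends to partners.

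Finally, a reader might infer that the same window wrongly misses harm from the screening bone marrow, because it opens only at first treatment while observational patients are covered for procedure-related events. The comparison fails. Observational reporting under Section 8.2.2 starts at registration, and the interventional baseline marrow is taken before registration. Sections 5.1 and 5.2 also allow baseline assessments to come from standard care or to be combined with local diagnostic procedures. That is not part of this point.

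**Conclusion.** The point holds as a gap in safety data collection. Pregnancies that begin from day 29 to about day 91 after the last dose lie inside the protocol's own contraception period but carry no duty of notification or outcome follow-up. The gap is about 63 of 91 days, or 69% of the post-treatment contraception period (67% to 70% depending on how three months is counted), and about 24% of treatment plus three months if six cycles are given. In that interval, only serious events that come to light and are judged at least possibly related to a trial drug remain reportable.

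The figures assume that both periods run from the same last dose. Few pregnancies are expected, and the determination of the maximum tolerated dose, which rests on toxicity in cycle 1, is not affected. The reason to act is that the protocol already treats pregnancy outcome as safety data and already has the forms for it.

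**What to change.** In Section 8.1.2.2, replace the reference to the SAE reporting period with a notification window of its own. It should run from the start of trial treatment to the end of the post-treatment contraception period that the protocol already sets in Sections 4.2 and 7.5.4. Outcome follow-up and the partner consent step stay as described. The change aligns data collection with an existing period and alters no treatment or contraception rule.

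The cost is one sentence in the protocol and a few extra Pregnancy Notification Forms. For most patients the existing follow-up of at least 12 months reaches far enough. Patients whose treatment continues so long that this minimum ends before the contraception period does would need one extra contact.
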